## 7.2 Secondary outcomes

### 7.2.1 Proportion of participants achieving clinical remission

The difference in the proportions of patients in clinical remission after 12 weeks of first-line methotrexate with T2T care will be calculated for comparisons between Arms A vs. B and Arms B vs. C. In addition, the difference in proportions of patients at 24 weeks will be calculated for Arm B vs Arm C only. Clinical remission will be deemed to have been achieved if  $DAS28ESR \leq 2.6$ . Details of the DAS28ESR score are given in section 7.1.

### 7.2.2 Differences in the medians of PROMs at Weeks 12 and 24

The differences in the medians of patient-reported outcome measures (EMS, VAS scales, HAQ-DI) after 12 & 24 weeks will be calculated between Arms A vs. B and Arms B vs. C.

The EMS is the Assessment of early morning stiffness and is the duration of morning stiffness reported by subjects as the average daily length during the past week in minutes (from time of waking to time of maximal improvement, up to a maximum of 720 minutes).

The four VAS scales reported are:

- Physician Global Assessment of general health: a Visual Assessment Score from 0 – 100mm on the patient's current disease activity. The 0 mm corresponds to no disease activity, 100mm corresponds to extremely active.
- Patient Assessment of General State of Health: a VAS from 0 to 100mm, the patient rates their general state of health. 0mm corresponds to 'very well' and 100mm to 'very poor'.
- Patient Assessment of Disease Activity: a VAS from 0 to 100mm, the patient rates how their arthritis is, with 0mm corresponding to 'very well' and 100mm to 'very poor'.
- Patient Assessment of Pain: a VAS from 0-100mm, rating their current pain, with 0mm being no pain and 100mm corresponding to the worst possible pain.

The Health Assessment Questionnaire Disability Index (HAQ-DI) is formed of 20 questions in 8 categories of functioning that represent different activities - dressing, rising, eating, walking, hygiene, reach, grip and usual activities. For each item there is a 4-level difficulty scale scored from 0-3, representing no difficulty (0), some (1) or much (2) difficulty, and unable to do (3). The highest component score in each category determines the category score, unless the patient uses aids or devices for, or receives assistance with activities in that category, in which case the relevant category score is increased to 2 if the maximum score was previously <2. Where 'other aids' are

collected, a list of these will be produced and the category which they will contribute towards will be agreed and documented prior to database lock.

The score for the disability index is the mean of the eight category scores. If more than two of the categories, or 25%, are missing, the scale, cannot be scored. If fewer than 2 of the categories is missing, the sum of the categories will be divided by the number of answered categories. The higher score indicates greater disability.

### **7.2.3 Differences in the proportion of participants achieving imaging remission at Week 24**

The difference in the proportions of patients in imaging remission (PD=0) at 24 weeks will be calculated between Arms A vs. B and Arms B vs. C.

Ultrasound assessment of power doppler synovitis (PD) will be performed at baseline and 24 weeks, as per standardised protocol on the standard set of 26 joints: Bilateral wrists, Metacarpal joints (MCP) 2 & 3, Proximal inter-phalangeal joints (2 & 3), Elbows, Knees, Ankles, Bilateral metatarsal joints (MTP) 1-5. Scans will be performed by the same dedicated ultra sonographer as per other clinical trials within the department at LIRMM.

PD will be scored between 0 and 3, with

- PD0 = no synovitis,
- PD1 = mild synovitis,  $\leq 3$  isolated single areas,
- PD2 = moderate synovitis,  $> 3$  isolated singles or confluent signal in less than half of the synovial area and
- PD3 = marked synovitis, signals in more than half of the synovial area.

Imaging remission will be determined if PD=0 (ie. No synovitis).

### **7.2.4 Difference in the proportion of participants achieving normalized T-cell status post-baseline**

The difference in the proportion of patients with normal naïve CD4+ T-cells at 24 weeks for patients with abnormal baseline naïve CD4+ T-cells receiving MTX with T2T care (Arm B) vs. etanercept + MTX (Arm C) will be calculated.

Naïve CD4+ T-cells will be measured via cell surface antigen detection by 8-colour flow cytometry. The CD4+ T-cells will first be identified by staining for the CD and CD4 markers. Naïve cells will be identified based on the high expression of CD45RB and positivity for CD45RA and CD62L. Also included in this panel will be T-regulatory cells (Treg) and inflammation related cells (IRC's).

Patients' naïve T-cell frequency (%) will be compared to the level expected for their age according to the following formula derived from 106 healthy controls [1]:  $(-0.54 * age) + 63.19$ .

A patient whose naïve T-cell level is at or above this value will be considered to have a normal T-cell result; a patient with levels below the age-expected value will be considered to have an abnormal result.

### **7.2.5 Difference in the proportion of participants achieving sustained clinical remission between study arms**

The difference in the proportions of patients in clinical remission (DAS28ESR  $\leq 2.6$ ) at both 12 and 24 weeks will be calculated for comparisons between Arms A vs. B and Arms B vs. C. The remission will be classified as sustained if the participant is in clinical remission at both time points. Details of DAS28ESR are given in section 7.1.

### **7.2.6 Difference in cumulative corticosteroid use up to and including Week 24 between study arms**

The difference in the average (mean and median) cumulative amount of corticosteroid use at 24 weeks between study arms (Arm A vs. Arm B and Arm B vs. Arm C) will be calculated. This includes any administered at the 24 week visit also.

Patients in either study arm may receive corticosteroid treatment (IM/IA or oral) at any of the follow-up study visits or at unscheduled visits if they have evidence of clinical flare i.e. do not meet target DAS28ESR<2.6. Administered doses will be in line with local standard clinical practice. For patients meeting the target DAS score but that have evidence of flare i.e. synovitis as per the assessing physician, corticosteroids may be offered. The name, dose and type of corticosteroid will be logged in the Concomitant Medications CRF when prescribed. Dose equivalent tables [2] for different types of steroids will be used to convert doses relative to 5mg of Methylprednisolone.

The cumulative dose of corticosteroid used by each participant will be calculated by summing over each type of steroid prescribed at each visit, including unscheduled visits, at which steroids were prescribed during follow-up.

### 7.3 Other collected variables

At baseline, other variables collected include:

- Demographics: Age(years), gender, ethnicity
- Concomitant medications/allergy history,
- Surgical/medical history,
- Family history,
- Smoking history,
- Anti-citrullinated protein antibody (ACPA) titre and status (positive/negative),
- Rheumatoid factor antibody (RF) titre and status (positive/negative),
- Anti-nuclear antibody (ANA) titre and status (positive/negative),
- Date of RA diagnosis,
- Vital signs

#### SDAI

Simple disease activity index (SDAI) for RA is composed of the numerical sum of five outcome parameters: TJC and SJC (28 joints), patient and physician's global assessment of disease activity (range 0-10) and level of CRP (mg/dL). Classic disease activity cut-offs define low disease activity as an SDAI  $\leq$ 11 and remission as a SDAI  $\leq$ 5. Scores range between 0-100 with 100 indicating greater disease activity. The equation is:

$$SDAI = TJC28 + SJC28 + PGA + PhGA + CRP$$

It will be calculated at baseline and weeks 4, 12 and 24.

#### CDAI

The Clinical Disease Activity Index (CDAI) is derived from SDAI but does not include measurement of acute phase response. The computation of the score is done through the following equation:

$$CDAI = TJC28 + SJC28 + PGA + PhGA.$$

It will be calculated at baseline and weeks 4, 12 and 24.

#### Safety

The number of patients experiencing SAEs and AEs, any clinically significant worsening of a pre-existing condition, an AE occurring from overdose (accidental or intentional) of an IMP, an AE

occurring from abuse of an IMP or an AE associated with the discontinuation of the use of an IMP will be recorded.

Biochemistry and haemotology parameters will be collected at all visits.

### **Imaging parameters**

Additional imaging parameters are collected at the same time as the PD including grey scale changes, erosions and osteophytes and tenosynovitis which are not covered in this SAP.

## **8. Data**

### **8.1 Case Report Forms**

The following CRFs are used in this study:

- Concomitant Medications
- Adverse Events
- Inclusion Criteria
- Exclusion Criteria
- Inclusion/Exclusion Criteria Met
- Informed Consent
- Randomisation and Study Meds
- Randomisation and Study Meds (wk4)
- Randomisation and Study Meds (wk12)
- Randomisation and Study Meds (wk 24)
- Changes in Medications
- Vital signs
- Medical History
- Physical Examination
- Screening Investigations
- Investigations
- T-cells
- TB testing
- Urine
- X-ray
- Examination – Systems
- Joint assessments
- Physician VAS
- Patient HAQ
- Patient VAS
- Disease Activity Scores
- Ultrasound

### **8.2 External datasets**

Each subject's screening will be recorded in the Subject Screening Log. The Investigator will keep a list containing all subjects enrolled into the study. This list remains with the Investigator and is used for unambiguous identification of each subject. The list contains the subject identification number, full name, date informed consent signed, date of screening, and the hospital number or National Health Security number, if applicable.

The subject's consent and enrolment in the study must be recorded in the subject's medical record. These data should identify the study and document the dates of the subject's participation.

The laboratory measurements to be collected in this study include haematology, clinical chemistry, pregnancy testing (for females of childbearing potential), urinalysis, CRP, ESR and immunological measurements (T-cell subsets). The blood will be drawn and sent to the laboratory in accordance with standard NHS practice. T-cell samples will be sent for flow-cytometry. Sample labels containing appropriate identification information will be provided. In addition to the above, a maximum of 40 mL of blood will be drawn and stored for exploratory soluble biomarker testing at baseline and week 24. Approximately an additional 25 mL will be collected at visits 2-5.

Data from screening logs and laboratory measurements etc. needed for analyses will be contained in the MACRO system.

#### **Protocol deviations**

A list of the protocol deviations will be provided as a .csv file to YTU at the end of the study to be used in the analysis. Any significant deviations from the protocol that may influence the viability of the data will be flagged in the provided file.

### **8.3 Management of database and data verification**

The research team is responsible for prompt reporting of accurate, complete, and legible data in the eCRF and in all required reports. Any change or correction to the electronic CRF will be time-stamped and documented within the data storage system. The Investigator will maintain a list of personnel authorized to enter data into the CRF.

Source documents are original records in which raw data are first recorded. These may include, but are not limited to, hospital/clinic/general practitioner records, charts, diaries, x-rays, laboratory results, printouts, pharmacy records, care records, or other printouts, completed scales, or Quality of Life Questionnaires. Source documents will be kept in a secure, limited access area.

Some data will be recorded directly in the CRF and will not appear in a physical source document (as defined in the Source Data Location Sheet document).

Source documents that are computer-generated and stored electronically will wherever possible be printed and filed in the patient medical notes for review by the monitor/inspector.

Source data will be transcribed into the eCRF, which also incorporates a validated electronic database, using a research data management system (MACRO). eCRF completion guideline documents are in place to highlight any data entry requirements and to minimise the need for queries. Computerized data cleaning checks will be used in addition to manual review to check for discrepancies and to ensure consistency of the data. Data will be entered into the research database using a rolling query-resolution system designed to identify data entry errors and protocol deviations in a timely fashion to allow accurate reconciliation.

An electronic audit trail system will be maintained within the MACRO system to track all data changes in the database once the data has been saved initially into the system or electronically loaded. Regular backups of the electronic data will be performed. A data export will be transferred to statisticians based in York trials unit via a University of Leeds OneDrive link.

## **9. Sample Size**

We will allocate the patients to arm A if the patient's naive CD4+ T-cell frequency is normal for their age and gender. In our previous pilot study 42% of comparable RA patients had abnormal frequency values, of whom 25% responded to MTX at 6 months compared to 68% of those with normal values.

Those with abnormal values will be (randomly permuted block) randomised 1:1 to arm B or C, therefore this would result in an approximate 2.75:1 ratio of patients in arms A and B. For the primary outcome of clinical remission at 24 weeks, at the 5% level of significance, to achieve 80% power to detect a difference between the target proportions of patients achieving clinical remission in arms A (68%) and B (25%) [3], a total of 53 patients would be required, assuming binary logistic regression with a variance inflation factor of 1.05 estimated from pilot data. We will increase the sample size to n=60 to account for 10% drop-out. The total number needed to be recruited to the study would therefore be 76 (44 in arm A, 16 in arm B and 16 in arm C). To have a more robust estimate of the proportion of clinical remission in arm B and C, recruitment will continue until at least 34 and no more than 60 patients with abnormal T-cell values have been randomised 1:1 to arm B or C, and there are at least 46 patients in arm A. Thus, the total sample size for the study is anticipated to be between 76 (approximately A=44, B=16, C=16) and 106 patients (approximately A=46, B=30, C=30). In the case where recruitment within Arm A is disproportionately recruiting more than Arm B or C, recruitment will stop within Arm A once minimum recruitment number has been reached.

## 10. Randomisation and blinding

The pharmacy at Chapel Allerton Hospital will prepare a randomisation schedule. A central randomisation method using randomly permuted block sizes will be used. Patients will be randomised if they are found to have abnormal T-cells. The Trials team at Leeds General Infirmary will hold the master randomisation list and, as patients enter the study, they will be assigned the next available Patient ID Number and assigned to receive treatment with either MTX + Etanercept or MTX with T2T care. Randomisation codes will remain blinded to clinicians recruiting to the study as these will be administered centrally.

## 11. Final analysis

### 11.1 Analysis software

Analyses will be conducted at the end of the trial using Stata 18 (*StataCorp, [name]*), or later (to be confirmed in final report) or R (version to be confirmed in final report).

### 11.2 Analysis principles and populations

For all analyses, unless otherwise stated, the analysis set will include all randomised participants. Analysis sets are given in Table 2.

*Table 2: Analysis data sets*

Analysis set	Description
Full analysis set (FAS)	The FAS will include all patients randomised and not withdrawn from the study prior to or during their baseline visit. Following the intent-to-treat principle, patients will be analysed according to the treatment assigned irrespective of treatment received.
Per protocol set (PPS)	The PPS will include patients in the FAS who have no significant deviations from the protocol that may influence the viability of the data.

Safety set	The Safety set will include all patients who took at least 1 dose of study treatment during the treatment period. Patients will be evaluated according to study treatment received.
------------	---

The full analysis set will be used for all efficacy analyses unless specified otherwise and the safety set for safety analyses. Statistical tests for the primary and secondary outcomes comparing Arm A vs Arm B will be two-sided at the 5% significance level and 95% confidence intervals (CIs) shall be used. For the secondary outcomes comparing Arm B vs Arm C, no inferential tests will be carried out.

Due to the lower limit of reliable CRP detection being 5; values less than 5 will be recorded as 0 in the data. It will be assumed these values were uniformly distributed between 0 and 5 and hence will be replaced as 2.5 in the calculation of any scores (for example in calculating SDAI).

In general, summary statistics [n (number of available measurements), arithmetic mean, standard deviation, median, minimum, and maximum] for quantitative variables and absolute and relative frequency tables for qualitative data will be presented.

A table template to illustrate this with the primary outcome measure is given in appendix 1.

### 11.2.1 Hypothesis

The primary alternative hypothesis is that the difference ( $\Delta$ ) in the proportions of patients in clinical remission (DAS28  $\leq$  2.6) after 6 months of first-line treatment with MTX monotherapy between those with normal (Arm A) vs. abnormal (Arm B) naive CD4+ T-cell frequencies will differ from 0.

$$H0: \Delta = 0$$

$$H1: \Delta \neq 0$$

The null hypothesis will be rejected if the p-value is less than 0.05.

### 11.2.2 Analysis visit windows

Visit windows will be used for all assessments unless specified otherwise. The actual day of an assessment will be mapped to the planned study visit using the following rules:

- If more than one assessment falls within a visit window, the closest non-missing assessment to the scheduled day will be used in the analysis.
- If more than one non-missing assessment actual dates are equidistant from the target day, the earlier assessment will be used in the analysis.

The windows for the analysis visits, split by the mid-point between the visits, are given in Table 3.

*Table 3: Analysis visit windows*

Timepoint	Study day	Analysis visit window in days
Week 0 (baseline)	1	All assessments prior to first dose of IMP
Week 4	29	Assessments post first dose of IMP to Day 57
Week 12	85	58 to 127
Week 24	169	$\geq 128$

The study day will be calculated as:

$$\text{Study day} = \text{Actual visit or assessment date} - \text{date of initial IMP dose} + 1$$

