9. STUDY PROCEDURES BY VISIT

Note: All timed visits post-screening should take place within a seven-day window of the scheduled visit time.

All study visits falling outside this window will be reported to the Sponsor QA Office on the designated protocol deviation form, in-line with the corresponding Sponsor SOP.

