9.4.6. Unscheduled visits

- For patients who do not tolerate their medication or are flaring outside of the study schedule.
- Will be recorded in the medical notes and in the CRF.
- If side effects related to IMP to be recorded as an adverse event
- Any changes to treatment to be documented

- **General**

- Assess compliance with treatment
- Clinical observations will be performed as per standard care (not required as a research parameter)
- Medication, allergy and co-morbidity check

- **Clinical assessment data**

- Physical examination if clinically indicated

- **Laboratory tests**

- Routine haematology and biochemistry suitable for diagnostic investigation & therapeutic DMARD monitoring FBC, U&E, LFT & eGFR ml/min/1.73 m²
- Urinalysis/pregnancy test if clinically indicated

- **Adverse event recording**

If the reason for the visit is a flare, the following assessments will also be done:

- **Clinical assessment data**

- Joint examination performed by an independent assessor:
 - Tender joint count (28)
 - Swollen joint count (28)
- Disease activity score (DAS28)
- Clinical disease activity index (CDAI)
- Simplified disease activity index (SDAI)
- Early morning stiffness (mins)

- **Laboratory tests**

- *Naïve CD4+ T-cells*
- ESR (mm/h) & CRP (mg/L)

- **Patient reported outcomes**

- Visual analogue scores of pain/disease activity/general health
- Physician assessment of general health
- HAQ-DI

- ***Imaging***

- o Power Doppler Ultrasound (PDUS) of standard set of 26 and 6 tendons joints for grey-scale (GS), power Doppler (PD), erosions (E) and osteophytes (O) and tenosynovitis (TSV)
- Management of DMARD treatment/administration of corticosteroid treatment will be at the discretion of the treating study physician

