### 11.2.3 Missing data

Individuals who discontinue study treatment will continue to be followed up, where possible, according to the study visit schedule. Patients who discontinue study treatment early due to lack of efficacy will be considered treatment non-responders from that point onward (not achieving clinical

or imaging remission). In the main analyses, patients with missing data for reasons other than lack of efficacy will also be considered non-responders. For patient-reported outcomes, the analysis will only include patients with data available.

Missing data for the baseline covariates which will be used in analyses (DAS28ESR, age, gender, smoking status) will be imputed with the mean or the modal value (for categorical variables). If there is a large amount of missing data for a covariate then it will be considered whether to remove the variable from analysis models.

For the analyses of the T-cell status, missing age will be imputed with the mean for the calculation of the threshold for normal T-cell status. If the T-cell frequency is missing then the status will be set to abnormal if the missing data is due to lack of efficacy, otherwise the status will be set to missing.

In cases where there are a lot of missing data in secondary outcomes, best and worst-case imputation may be considered as ad-hoc analyses to assess the impact of exclusion.

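### SAP 11.2.2 gives the scheduled visit no priority, so an unscheduled flare assessment can replace a valid, in-window Week 24 (or Week 12) DAS28ESR

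*SAP*

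**What the plan says.** SAP 11.2.2 sets a broad scope: "Visit windows will be used for all assessments unless specified otherwise". Within a window the nearest value wins: "If more than one assessment falls within a visit window, the closest non-missing assessment to the scheduled day will be used in the analysis". Ties are settled by date: "If more than one non-missing assessment actual dates are equidistant from the target day, the earlier assessment will be used in the analysis". The boundaries are described as follows: "The windows for the analysis visits, split by the mid-point between the visits, are given in Table 3". Table 3 gives Week 12 as days 58 to 127 (target day 85) and Week 24 as day 128 onward (target day 169), with no last day. Study day is counted from the "date of initial IMP dose".

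The protocol is much tighter on conduct. Section 9 states: "All timed visits post-screening should take place within a seven-day window of the scheduled visit time". Section 9.4.6 provides unscheduled visits: "For patients who do not tolerate their medication or are flaring outside of the study schedule". When the reason is a flare, that section and the schedule in 9.1 add joint counts, DAS28, ESR and the VAS scales. SAP 6.7 also lists DAS28 among the data from unscheduled visits.

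On missing outcomes, SAP 11.2.3 says that in the main analyses "patients with missing data for reasons other than lack of efficacy will also be considered non-responders". The estimand in SAP 11.5.1 is remission at 24 weeks.

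**The concern.** The scheduled Week 24 visit is the planned measurement of the primary outcome. Under SAP 11.2.2 it is only one candidate among all assessments from day 128 onward. An unscheduled flare visit is another, because it yields a complete DAS28ESR.

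The two kinds of visit are not interchangeable. The scheduled visit happens because of the calendar; the flare visit happens because disease activity has risen. Protocol 1.2.2.2 and SAP 7.2.6 describe flare chiefly as failing to meet the DAS28ESR target of below 2.6. Letting a flare visit stand in for a valid scheduled visit therefore chooses the value partly on the outcome being measured. The usual effect would be to record a patient who was in remission at the planned visit as not in remission.

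SAP 11.6.1 analyses Week 12 remission in the same way, and sustained remission needs both time points, so a displaced value at either one changes it. A smaller, separate consequence is that the open window decides who counts as missing at Week 24, and so who is imputed as a non-responder.

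**Working it through.** **1. The plan's own boundaries.** Mid-points of the target days in Table 3: (29 + 85)/2 = 57 and (85 + 169)/2 = 127. These reproduce Table 3, so the windows are as intended.

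**2. The protocol's window in study days.** 169 ± 7 gives days 162 to 176 (15 days); 85 ± 7 gives days 78 to 92. This takes day 1 as the start of treatment and dates the visits from it.

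**3. When a scheduled visit is displaced.** With the scheduled visit on day s and an unscheduled DAS28ESR on day u, the rule selects u if |u − target| < |s − target|, or if the distances are equal and u is earlier.

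| Scheduled visit | Distance from target | Unscheduled days that replace it |
|---|---|---|
| Week 24 on day 169 | 0 | none |
| Week 24 on day 173 | 4 | 165 to 172 |
| Week 24 on day 176 (in window) | 7 | 162 to 175 |
| Week 24 on day 162 (in window) | 7 | 163 to 175 |
| Week 24 on day 183 (late) | 14 | 155 to 182 |
| Week 12 on day 92 (in window) | 7 | 78 to 91 |
| Week 12 on day 78 (in window) | 7 | 79 to 91 |

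Example: flare visit on day 163, Week 24 visit in remission on day 176. |163 − 169| = 6 is less than |176 − 169| = 7, so the flare value becomes the primary outcome.

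**4. Which routes are realistic.** No study visit is scheduled after Week 24, so the likely route there is a flare visit followed by a scheduled visit after day 169. At Week 12 follow-up continues, so displacement can run in either direction. Protocol 9.3 lets treatment start up to 7 days after the baseline clinic visit. If visits are dated from that clinic visit and treatment starts L days later (an assumption), the in-window Week 24 days become 162 − L to 176 − L. At L = 7 that is days 155 to 169, and no in-window visit falls after the target day. The day-176 example therefore needs little or no lag.

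**5. Size per patient.** One patient is 1/16 = 6.25 points of Arm B, or 1/30 = 3.3 points at the upper planned size. In Arm A it is 1/44 = 2.3 points.

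**6. Direction.** At the planning rates in SAP section 9, expected remitters are 0.68 × 44 ≈ 30 in Arm A and 0.25 × 16 = 4 in Arm B. If fractions fA and fB of remitters are recoded, the difference changes by −0.68 fA + 0.25 fB. It widens only if fB/fA exceeds 0.68/0.25 = 2.72, and otherwise narrows or stays the same. The documents give neither fraction.

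Illustration only, assuming equal fractions f, so that the difference is 0.43 × (1 − f). Power is for the two-proportion comparison with A=44 and B=16, two-sided 5%, without the variance inflation factor:

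| f | Difference | Power |
|---|---|---|
| 0 | 43.0 points | 87% |
| 5% | 40.9 points | 83% |
| 10% | 38.7 points | 79% |
| 20% | 34.4 points | 68% |

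**7. Missing Week 24 visit.** Day 128 is (128 − 1)/7 = 18.1 weeks after day 1, 169 − 128 = 41 days before target, and 162 − 128 = 34 days before the earliest in-window day. If the only value in the window is above 2.6, the patient is a non-remitter, exactly as under imputation. If it is 2.6 or below, the patient counts as a 24-week remitter instead of a non-responder.

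**The case against.** Mid-point windows with a nearest-to-target rule are prespecified, deterministic, the same in every arm, and retain observed data. The ±7 days governs visit conduct, so a wider analysis window is not a contradiction. This stands. Nor does window width cause the main problem: displacement on days 162 to 176 would occur unchanged under the protocol's own window. The cause is the lack of priority for the scheduled visit.

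SAP 11.2.2 never names unscheduled visits, whereas SAP 7.2.6 includes them expressly for corticosteroid use. Their eligibility is thus an inference from a rule covering all assessments. That is fair, but the text contains no exclusion, and two programmers could reasonably implement it differently for the primary endpoint.

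The deviation list and the per-protocol analysis give some protection against out-of-window visits, where the deviation is flagged as significant. They do not address displacement, because an unscheduled flare visit is permitted and need not be a deviation. None of the sensitivity analyses in SAP 11.5.1.1 varies the choice of visit.

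A reader might infer three stronger things that the documents do not support:

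- That the rule penalises Arm B and inflates the A versus B difference. Arm A has about 30 expected remitters who could be recoded against about 4 in Arm B, and no flare rates are given.
- That non-responder imputation is bypassed for anyone with a DAS28ESR after day 127. Most assessments between Weeks 12 and 24 would be flare visits, and a value above 2.6 gives the same result as imputation.
- That stopping Benepali at the end of the study contaminates the primary outcome through late visits. Arm C is not in the primary comparison, B versus C has no inferential tests, and no study visit is scheduled after Week 24.

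**Conclusion.** The point holds. As written, SAP 11.2.2 allows a flare-triggered assessment to replace a complete, protocol-compliant Week 24 or Week 12 visit, and so allows the outcome to influence which value is analysed. The main effect is to recode remitters as non-remitters. The number of patients affected and the net direction between Arms A and B cannot be determined from the documents; the power figures above illustrate one assumed pattern and are not estimates.

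The open Week 24 window is secondary: it matters only when the scheduled value is missing and the substitute is a remission value, from as early as day 128 or from a very late visit.

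The conclusion assumes that unscheduled visits are eligible because nothing excludes them, and that day 1 in Arms A and B is the start of methotrexate. The latter is needed because Benepali is the only IMP, so the stated origin does not literally apply to those arms; that is a separate gap.

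**What to change.** In SAP 11.2.2, state that the scheduled Week 12 or Week 24 visit is used whenever it has a non-missing DAS28ESR, and that an unscheduled assessment is considered only when the scheduled value is missing.

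Set an upper limit for the Week 24 window, beyond which the outcome is missing and follows 11.2.3. The width is the sponsor's choice, since the documents do not point to one value. Fix it before the arm codes are released; Protocol 12.10 already provides for a SAP update at that stage.

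List by arm the patients whose Week 24 value comes from an unscheduled visit or from outside the protocol's ±7 days.

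The cost is a few sentences in the SAP, minor programming and one listing. The downside is that a few patients with only a very late value become non-responders in the primary analysis.
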